### 5.6.4 Vital Signs

Vital signs at each visit and change from baseline to each visit will be summarized using descriptive statistics for each study intervention group. The baseline value of any variable will be defined as the last value recorded prior to the first administration of study intervention. Participants with a missing baseline value will not be summarized for that variable.

### 5.6.5 Physical Examinations

Physical examination data will not be summarized because any significant finding will be reported and summarized as an AE.

## 5.7 Patient-Reported Outcomes Analysis

For participants enrolled into the Advanced Prostate Cancer cohort, an exploratory analysis may be performed with the patient-reported dataset collected via ApricityCare™, including but not limited to the frequency with which participants complete the daily symptom survey in ApricityCare™, and the frequency of Apricity website access by investigative sites.

## 5.8 Missing Data

### 5.8.1 Missing and Partial Missing Adverse Event Dates

If the AE start date is not a complete date, the following rules will be applied to determine whether the event is treatment emergent.

- If the start date is completely missing: The AE will be considered treatment emergent unless the AE stop date is earlier than the date of first dose of study intervention.
- If the day of the AE start date is missing:
  - If the month and year of the start date are later than the month and year of the date of first dose of study intervention, then the AE will be considered treatment emergent.
  - If the month and year of the start date are equal to the month and year of the date of first dose of study intervention and the stop date is unknown or later than the date of first dose of study intervention, then the AE will be considered treatment emergent.
- If the day and month of the start date are missing:
  - If the year of the start date is later than the year of the date of first dose of study intervention, then the AE will be considered treatment emergent.
  - If the year of the start date is equal to the year of the date of first dose of study intervention and the stop date is unknown or later than the date of first dose of study intervention, then the AE will be considered treatment emergent.

#### 5.8.2 Missing and Partial Missing Death Dates

For death dates, the following conventions will be used for imputing partial dates:

- If the date of death is completely or partially missing, but there is an AE with the outcome as 'Fatal', the date of death will be replaced by the end date of the AE.
- If only the day of the month is missing and there is no AE with outcome as 'Fatal', the 1st of the month will be used to replace the missing day. The imputed date will be compared to the last known date alive plus 1 day, and the maximum will be considered as the death date.
- If the month or the year is missing, the death date will be imputed as the last known date alive plus 1 day.
- If the date is completely missing but the reason for death is present, the death date will be imputed as the last known date alive plus 1 day.

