- The most appropriate diagnosis or, if a diagnosis cannot be established, the abnormal laboratory values should be recorded on the Adverse Event eCRF page and reported to the Sponsor immediately as an SAE.

Lack of Efficacy or Worsening of Underlying Disease

- Events that are clearly consistent with the expected pattern of progression of the underlying disease should not be recorded as AEs. These data will be captured as efficacy assessment data only. In most cases, the expected pattern of progression will be based on RECIST. In rare cases, the determination of clinical progression will be based on symptomatic deterioration. However, every effort should be made to document progression through use of objective criteria. If there is any uncertainty as to whether an event is due to disease progression, it should be reported as an AE.

Deaths

- All deaths that occur during the protocol-specified AE reporting period, regardless of relationship to study intervention, must be recorded on the Death eCRF page and immediately reported to the Sponsor (see [Section 8.3.1](#)), unless the death is attributed to progression of disease.
- Death should be considered an outcome and not a distinct event. The event or condition that caused or contributed to the fatal outcome should be recorded as the single medical

concept on the Adverse Event eCRF page. Generally, only one such event should be reported.

- If the cause of death is unknown and cannot be ascertained at the time of reporting, “unexplained death” should be recorded on the Adverse Event eCRF page.
- If the cause of death later becomes available (eg, after autopsy), “unexplained death” should be replaced by the established cause of death.
- The term “sudden death” should not be used unless combined with the presumed cause of death (eg, “sudden cardiac death”).
- If the death is attributed to progression of underlying disease, “underlying disease” should be recorded on the Death eCRF page; no SAE form is necessary.
- Deaths that occur after the AE reporting period should be reported as described in [Section 8.3.2](#).

Pre-existing Medical Conditions

- A pre-existing medical condition is one that is present at the baseline visit for this study. Such conditions should be recorded on the General Medical History and Baseline Conditions eCRF page.

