##### 5.4.2.2 Progression-Free Survival

Progression-Free Survival (PFS) is defined as the time from initiation of study intervention to the date of first documented radiographic progression of disease or date of death due to any cause, whichever occurs first. Participants who continue treatment beyond initial disease progression will be considered to have progression of disease (PD) at the time of the initial progression event.

Participants who do not have radiographic PD at the time of analysis will be censored as follows:

- Participants who do not have radiographic PD and are still on study at the time of analysis will be censored at the date of the last tumor assessment documenting absence of progressive disease.
- Participants who have discontinued study treatment and have started subsequent anti-cancer therapy or had subsequent cancer surgery or radiation prior to documentation of radiographic PD will be censored at the date of the last evaluable tumor assessment prior to the initiation of subsequent treatment.

- Participants who discontinued the study prior to documentation of radiographic PD will be censored at the date of the last tumor assessment documenting absence of progressive disease.
- Participants who do not have radiographic PD and who die more than 16 weeks from their last evaluable tumor assessment will be censored at the date of the last tumor assessment documenting absence of progressive disease. Participants who die within 16 weeks of their last evaluable tumor assessment will be considered as having an event at the date of death.

PFS will be estimated using Kaplan-Meier techniques, and the median survival time and 95% CIs will be estimated within each study intervention group.

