#### 5.4.2.3 Overall Survival

Overall Survival (OS) is defined as the time from initiation of study intervention until death due to any cause. Participants who are not reported as having died at the time of analysis will be censored at the most recent contact date they were known to be alive. See Section 5.8.2 for handling of missing or partial death dates.

OS will be estimated using Kaplan-Meier techniques, and the median survival time and 95% CIs will be estimated within each study intervention group.

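### SAP 5.8.2 ignores a recorded year of death when the month is missing, so a few deaths can be imputed into a year the record rules out, and OS can be understated for those participants

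*SAP*

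**What the plan says.** SAP section 5.8.2 gives four rules for incomplete death dates.

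1. If an adverse event (AE) with a fatal outcome is on record, "the date of death will be replaced by the end date of the AE".
2. If only the day is missing and there is no fatal AE, the first of the recorded month is tried: "The imputed date will be compared to the last known date alive plus 1 day, and the maximum" is taken.
3. "If the month or the year is missing, the death date will be imputed as the last known date alive plus 1 day".
4. If the whole date is missing but a reason for death is present, the date is again the day after the participant was last known alive (LKA + 1).

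Two endpoints depend on the result. The OS section (SAP 5.4.2.3) refers to these rules directly: "See Section 5.8.2 for handling of missing or partial death dates". The PFS section (SAP 5.4.2.2) uses the date of death to decide event status for participants without radiographic progression. Those "who die more than 16 weeks from their last evaluable tumor assessment will be censored", and on the other side of the limit: "Participants who die within 16 weeks of their last evaluable tumor assessment will be considered as having an event at the date of death". SAP 5.8.2 is the only convention given for an incomplete death date.

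**The concern.** Rule 3 treats a death recorded as, say, 2021 exactly like a death with no date at all. The recorded year is neither used nor checked. Rule 2 treats the recorded month and year as a floor. The AE rules in SAP 5.8.1 also use a recorded year when day and month are missing. Only the partial death date discards it.

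If the participant was last known alive in an earlier calendar year, following rule 3 exactly can give a date that contradicts the data. The error has one direction: the death is placed earlier than the record allows. OS time is therefore shortened for that participant. In principle the PFS status could change as well, if the misplaced date falls on the other side of the 16-week limit.

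**Working it through.** The plan states no figure on this point, so there is none to reproduce. The check is date arithmetic.

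**Inputs**
- Rule 3: D = LKA + 1 day (SAP 5.8.2).
- Comparison rule, which extends rule 2 to a known year Y: D* = max(LKA + 1 day, 1 January of Y).
- Survival contact every 3 months, window ± 7 days, for up to 2 years from last dose (Protocol 1.3, Tables 1–4).
- Public records may be used for survival status (Protocol 7.2).
- PFS limit: 16 weeks = 112 days (SAP 5.4.2.2).
- The calendar dates below are illustrative assumptions.

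**Shift in OS.** D* − D is the smallest understatement that is certain from the record. For a death recorded as 2021, month missing:

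| Last known alive | Rule 3 date | Rule 3 year contradicted | D* | Shift (days) |
|---|---|---|---|---|
| 20 Dec 2020 | 21 Dec 2020 | yes | 1 Jan 2021 | 11 |
| 31 Dec 2020 | 1 Jan 2021 | no | 1 Jan 2021 | 0 |
| 1 Nov 2020 | 2 Nov 2020 | yes | 1 Jan 2021 | 60 |
| 1 Oct 2020 | 2 Oct 2020 | yes | 1 Jan 2021 | 91 |
| 25 Sep 2020 | 26 Sep 2020 | yes | 1 Jan 2021 | 97 |
| 1 Mar 2020 | 2 Mar 2020 | yes | 1 Jan 2021 | 305 |
| 1 Feb 2021 | 2 Feb 2021 | no | 2 Feb 2021 | 0 |

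The inconsistency is plain in the 1 October row. With the same last contact, a death recorded as January 2021 with the day missing is dated 1 January 2021 under rule 2. With 2021 alone it is dated 2 October 2020 under rule 3.

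**Bound under kept contact.** Taking 3 months as 91 days and adding the 7-day window gives a longest gap of 98 days. That is the 25 September row, a shift of 98 − 1 = 97 days. If one contact came 7 days early and the next 7 days late, the gap would be 105 days and the shift 104, so 97 is approximate.

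**Share affected.** Assume last contact is uniform over 365 days and the gap to death is uniform over 1 to 98 days. A gap of g days crosses a year end for g of the 365 contact days, so the share is the mean gap over 365: [(1 + 98)/2]/365 = 49.5/365 = 13.6%. A full count over all pairs gives the same share, with a mean shift of 32 days and a maximum of 97 among the crossing deaths. With a gap of 1 to 91 days the share is 46/365 = 12.6%.

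**PFS.** Three illustrative cases, each with death recorded as 2021:

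| Last assessment | Last known alive | Weeks, rule 3 | Weeks, D* | PFS status |
|---|---|---|---|---|
| 1 Sep 2020 | 10 Dec 2020 | 101/7 = 14.4 | 122/7 = 17.4 | event → censored |
| 20 Aug 2020 | 1 Nov 2020 | 74/7 = 10.6 | 134/7 = 19.1 | event → censored |
| 1 Oct 2020 | 10 Dec 2020 | 71/7 = 10.1 | 92/7 = 13.1 | event both ways |

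Status changes only when day 112 lies between the two dates.

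**The case against.** Several limits on the point are fair and stand.

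- **The fatal-AE rule comes first.** Deaths in the AE reporting period, which runs to 100 days after last dose, normally have the causal event on the AE page. Rule 3 then matters mainly for later deaths and for deaths from progression. For the latter, Protocol 10.5.5 says the cause "should be recorded on the Death eCRF page; no SAE form is necessary", so a fatal AE will usually be absent.
- **Most year-only deaths are not contradicted.** When last contact falls in the year of death, LKA + 1 is consistent with the record. A reader might infer that rule 3 makes OS wrong in general. The documents support only that it can understate OS for some participants.
- **Very large shifts need missed contacts.** Last known alive on 15 March 2021 with death recorded as 2022 gives a date 291 days too early to be possible. But about three consecutive 3-monthly contacts would have to be missed. It is a possible case, not a typical one.
- **The PFS route is narrow.** It needs no radiographic progression, no subsequent therapy (those participants are already censored at an earlier scan) and a limit lying between the two dates. Scans about every 8 weeks until progression or new therapy make that uncommon. A reader might infer that PFS is materially affected, but nothing in the documents shows it.
- **Frequency is unknown.** Quarterly calls tend to narrow the month of death, and nothing says that public records give only a year. At 13.6%, about 1/0.136 = 7.4 year-only deaths without a fatal AE would be needed to expect one that crosses a year end.

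None of this removes the defect in the text. Followed as written, rule 3 can produce a date that the record excludes.

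**Conclusion.** The rule is wrong as written, at low severity. The error arises when four conditions hold together: no AE with a fatal outcome, a known year, a missing month, and last contact in an earlier calendar year (other than 31 December of the year just before). In that situation OS is understated by at least the distance from LKA + 1 to 1 January of the recorded year.

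The 97-day bound rests on kept contact, and the 13–14% share also on the uniform-gap assumption. Longer shifts, such as 305 days in the table, need missed contacts or a late finding in records. A change of PFS status is possible but should be rare.

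OS and PFS are secondary endpoints, summarised by Kaplan-Meier medians within group, in a study that SAP 5.4 says is not intended for hypothesis testing. There is no evidence that a reported median would change.

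**What to change.** Replace the third rule of SAP 5.8.2 with wording such as:

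> *If the year is known but the month is missing and there is no AE with outcome Fatal, impute 1 January of that year, compare it with the day after the last known date alive, and use the later of the two. If the year is missing, use the day after the last known date alive.*

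Add that PFS uses the same imputed date. The fatal-AE condition makes explicit the precedence that rule 2 states and rule 3 leaves to be inferred.

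The cost is one sentence in the SAP and one line of code. Every case in which rule 3 already agrees with the recorded year keeps its date. The floor is still the earliest possible date, so it removes impossible dates but not the general tendency of such imputation to place deaths early. The change should be made before the analysis, so that no contradictory date has to be settled afterwards.

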#### 5.9 Interim Analyses

Ongoing monitoring for safety and futility will be implemented based on the method of Thall and colleagues (Thall et al, 1995) separately in the CD8 high and CD8 low tumor groups for advanced metastatic cancer and advanced prostate cancer participants. Monitoring will be ongoing during enrollment in each group, once a participant receives treatment and their first treatment biopsy is performed. Screening and accrual to each group will continue until

sufficient information is available to assess the stopping rules as defined in the protocol Section 9.3.

## **6 DIFFERENCES COMPARED TO PROTOCOL**

The Protocol defines the secondary endpoint exploration of baseline CD8 counts association with CBR and with OS; this was removed from the SAP and will not be analyzed.

## 8 APPENDICES

### 8.1 Protocol Synopsis

**Protocol Title:**

An Exploratory Study of Nivolumab with or without Ipilimumab According to the Percentage of Tumoral CD8 Cells in Participants with Advanced Metastatic Cancer

**Short Title:**

Treatment with Nivolumab and Ipilimumab or Nivolumab Alone According to the Percentage of Tumoral CD8 Cells in Advanced Metastatic Cancer

**Rationale:**

The aim of this study is to provide a prospective classification of CD8 high (immunologically “hot”) versus CD8 low (immunologically “cold”) tumors at the time of treatment, based on the percentage of CD8 cells in a tumor biopsy, and to address the predictive value of the CD8 biomarker for selecting patients for treatment with nivolumab with or without ipilimumab.

**Key Objectives and Endpoints:**

| Objectives                                                                                                                                                                                                                                                                                                                                                                                                                                              | Endpoints                                                                                                                                                                                                                                                                                              |
|---------------------------------------------------------------------------------------------------------------------------------------------------------------------------------------------------------------------------------------------------------------------------------------------------------------------------------------------------------------------------------------------------------------------------------------------------------|--------------------------------------------------------------------------------------------------------------------------------------------------------------------------------------------------------------------------------------------------------------------------------------------------------|
| 
Primary
 
 
• To determine the clinical benefit rate (CBR) of nivolumab with or without ipilimumab in participants with advanced metastatic cancer, including advanced prostate cancer.
 
• To assess the proportion of participants in the nivolumab plus ipilimumab arm whose tumors will change from CD8 low to CD8 high as measured by a change in the percentage of tumoral CD8 cells.
 
 | 
 
• CBR is the proportion of participants who show clinical benefit, defined as CR, PR, or SD for <math>\geq 6</math> months as best response by RECIST v1.1.
 
• Change in the percentage of CD8 cells in on-treatment biopsies from baseline.
 
 |
| 
Secondary
 
 
• To determine the safety and tolerability of nivolumab with or without ipilimumab in participants with advanced metastatic cancer, including advanced prostate cancer.
 
• To determine the ORR of nivolumab with or without ipilimumab in participants
 
                                                                                                                      | 
 
• Incidence and severity of AEs based on CTCAE v5.0.
 
• ORR: Defined as CR or PR as best response by RECIST v1.1 assessment.
 
• PFS: Defined as the time from initiation of study therapy to date of first
 
                           |

| Objectives                                                                                                                                                                                                                                     | Endpoints                                                                                                                                                                                                     |
|------------------------------------------------------------------------------------------------------------------------------------------------------------------------------------------------------------------------------------------------|---------------------------------------------------------------------------------------------------------------------------------------------------------------------------------------------------------------|
| with advanced metastatic cancer, including advanced prostate cancer. 
 
To assess the association of percentage of CD8 infiltration in tumor samples with clinical outcomes (ORR, PFS, and OS).
 
 | documented progression of disease or date of death due to any cause. 
 
OS: Defined as the time from initiation of study therapy until death due to any cause.
 
 |

AE = adverse event; CBR = clinical benefit rate; CR = complete response; CTCAE = Common Terminology Criteria for Adverse Events; ORR = objective response rate; OS = overall survival; PFS = progression-free survival; PR = partial response; RECIST = Response Evaluation Criteria in Solid Tumors; SD = stable disease.

### Overall Design:

This is an open-label, exploratory study to evaluate nivolumab with or without ipilimumab based on percentage of tumoral CD8 cells at the time of treatment in participants with varying advanced solid tumors. Participants who have a tumor with  $\geq 15\%$  CD8 cells (classified as CD8 high) will receive nivolumab monotherapy, and participants who have a tumor with  $< 15\%$  CD8 cells (classified as CD8 low) will receive ipilimumab in combination with nivolumab.

### Number of Participants:

A total of up to approximately 200 participants will be treated. Beginning with Amendment 2, enrollment will be limited to tumor types known to be responsive to immunotherapy, have high prevalence ( $> 20\%$ ) CD8  $\geq 15\%$  tumors, and/or have been observed in the study to have tumors transition from CD8 low to CD8 high following initiation of immunotherapy. Beginning with Amendment 3, a total of approximately 20 participants with advanced prostate cancer and tumoral CD8  $< 15\%$  will be randomly allocated to 1 of 2 cohorts using combinations of ipilimumab and nivolumab. Advanced prostate cancer participants with tumoral CD8  $\geq 15\%$  will be enrolled in the nivolumab monotherapy arm. Ongoing monitoring for safety and futility will be implemented based on the method of Thall and colleagues (Thall et al, 1995) separately in the CD8 high and CD8 low tumor groups.

### Intervention Groups and Duration:

Advanced Metastatic Cancer: Single-agent nivolumab will be administered at 360 mg intravenously (IV) every 3 weeks (Q3W). Participants who continue to show clinical benefit after the first disease assessment will receive nivolumab 480 mg IV every 4 weeks (Q4W) until progressive disease (PD) or intolerable toxicity. At PD, participants will be allowed to crossover to the CD8 low arm of ipilimumab (1 mg/kg) and nivolumab (360 mg).

For nivolumab and ipilimumab combination therapy, nivolumab will be administered at 360 mg IV Q3W, and ipilimumab will be administered at 1 mg/kg IV Q3W for the first 2 doses and then every 6 weeks for the 3rd and 4th doses, followed by nivolumab 480 mg IV Q4W until PD or intolerable toxicity. After receipt of the first dose of ipilimumab, the Investigator may determine (based on clinical symptoms) the number of future doses of ipilimumab the participant will receive, for a maximum of 4 doses. Participants who stop ipilimumab dosing early due to toxicities, may start nivolumab maintenance (ie, 4 doses [12 weeks] of nivolumab following the first dose).

Advanced Prostate Cancer (Amendment 3): Single-agent nivolumab administered at 360 mg intravenously (IV) every 3 weeks (Q3W). Participants who continue to show clinical benefit after the first disease assessment will receive nivolumab 480 mg IV every 4 weeks (Q4W) until progressive disease (PD) or intolerable toxicity. At PD, participants will be allowed to crossover to the advanced prostate cancer CD8 low arm of ipilimumab (3 mg/kg) and nivolumab (1 mg/kg).

For nivolumab and ipilimumab combination therapy, CD8 low arm will be randomly allocated into 1 of 2 cohorts, using different doses of ipilimumab administered in 6-week cycles. Prostate Cohort A will receive nivolumab 1 mg/kg Q3W and ipilimumab 3 mg/kg every 6 weeks (Q6W) for 2 cycles, then nivolumab maintenance 480 mg Q4W until PD or intolerable toxicity. Prostate Cohort B will receive nivolumab 1 mg/kg Q3W and ipilimumab 5 mg/kg Q6W for 2 cycles, then nivolumab maintenance 480 mg Q4W until PD or intolerable toxicity.

